**3. Reach a stimulation intensity of 100 mA without a blood pressure response or intolerable symptoms.**

### **Risk and Discomforts:**

- Heart Rate, Arterial Stiffness and Blood Pressure: These are non-invasive procedures that involve minimal risk; however, some participants may experience discomfort when the ECG electrodes are removed from the skin and when the blood pressure cuffs are inflated.
- Transcutaneous stimulation: Participants may get headaches, autonomic dysreflexia, skin breakdown at the electrode placement site, pain, severe contractures (fractures) and muscle tears. If any of these potential risks occur, the stimulation will cease immediately and the investigators will monitor the situation.

As with any research, there may be unforeseen risks and discomforts. [name], a medical doctor associated with the study, will be available and present during testing to for clinical intervention if necessary or to treat any medical emergency.

### **Study Compensation:**

Participants will be given a study compensation of \$100 for each study visit (9 total visits); participants could earn a total of \$900 for completing all study visits.

### **Costs:**

This protocol has been funded by VA Research and Rehabilitation and all costs associated will be covered by this grant.

### **Publication of Research:**

It is anticipated that the observations made in this study will be presented at National and International meetings and will be submitted for publication in peer-reviewed journals, including those in the fields of Spinal Cord Medicine and neurology.

Targeted Transcutaneous
Stimulation to Restore Autonomic
Cardiovascular Health in Veterans
with Spinal Cord Injury

NCT05180227

August 18, 2025

Statistical analysis plan:

The primary outcome variable will be systolic blood pressure. Data will be analyzed with a mixed-modeling approach to determine which stimulation parameters consistently yield increases in systolic blood pressure. Participant will be modeled as a random effect and stimulation characteristics as fixed effects including: cathodal stimulation site (T7/8, T9/10, T11/12, and L1/2); stimulation frequency (30, 60, 120 Hz); waveform (monophasic, biphasic, asymmetric biphasic); pulse width (40 - 1000 μ s); carrier frequency (0, 10kHz); and stimulation current (0–120mA). To quantify the effect size of each participant's optimal tSCS parameters, each participant's blood pressure response will be compared to baseline blood pressure to calculate Cohen's d and confidence intervals. All analyses will be performed using R software. The lme4 package will be used to perform the mixed-models analyses for the ratio-scale data. The ordinal package in R will be used to analyze the Likert-scale-type data. The 95% level of confidence will be used. We used the R software simr package for multi-level models for power calculations with fixed effects variables of waveform and electrode site. Given the number of repeated measurements of SBP in each participant, we anticipate having *95% power to detect <2-mm-Hg mean differences at the 95% level of confidence.

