## **Hypotheses:**

1. We hypothesize that electrode placement at the lower thoracic (T7/8) and 50 mA current will be the optimal parameters to increase cardiovascular function.
2. We hypothesize that seated systolic BP will significantly increase following optimal TSCS.

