## Research Design and Methods

### Study Participants

**Study Participants:** It is our goal to recruit 12 eligible hypotensive individuals with injuries T6 and above. We anticipate recruitment of

4-5 eligible individuals each year of the project. Individuals with SCI will be recruited from the Northern New Jersey SCI Model System database via study solicitation flyer distribution at support groups and inpatient and outpatient treatment facilities.

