### Methods & Procedures:

We aim to compare stimulation parameters (frequency and amplitude, 1-ms pulses) using a monophasic waveform for different spinal segment sites to modulate BP. Sites for stimulation during a series of seated experiments will include 1) T 7/8; 2) T 9/10; 3) T11/12; and 4) L1/2, while beat-to-beat seated BP is continuously monitored and recorded in hypotensive individuals with SCI.

This study will take approximately 7-study visits, between 1-3 hours, per subject. Participants will be asked to arrive between 8:00 am and noon at the James J Peters VA Medical Center (JJP VAMC), after a normal breakfast and a good night sleep. The participants will be asked to not drink alcohol or caffeine 12 hours prior to their visit and there will be at least 3 days between study visits.

Approach: We will compare the electrode placement sites and amplitude during seated rest to modulate BP. We anticipate that BP responses will vary among the participants regarding the location of the electrode placement site and signal amplitude. Participants will visit the laboratory 8 times: visit 1): informed consent and medical intake to determine eligibility for enrollment in the study. Visits 2-8: amplitude (mA) mapping sessions at each electrode placement site (randomized), with continuous beat-to-beat BP monitoring at the finger arteriole and at 1-minute intervals at the brachial artery.

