Amplitude Parameter Mapping Visits 2-8: Before TSCS, electrodes will be placed on the vertebral midline at the spinous process (T7/8, T9/10, T11/12, L1/2), and the active site will be randomized. Each visit, we will complete one electrode placement site. Amplitude ramping will start at 10mA, with 10mA increments (pulse width, 1ms, frequency 30 Hz as shown (13)). Continuous real-time BP and heart rate will be measured for 5-minutes, before, during and after stimulation. During ramping, amplitude will stop increasing when SBP reaches optimal SBP between 110-120 mmHg (100-120 mmHg females) or reaches 100 mA with no SBP response (see below TSCS decision Tree). Amplitude will be decreased in 10 mA decrements in stimulation. BP will be continuously recorded during the rest period. Bilateral muscle activation (rectus femoris, medial hamstring, and gastrocnemius) will be monitored during all experiments to determine if skeletal muscle contractions are contributing to increases in BP. Additionally, signs and symptoms of autonomic dysreflexia will be monitored during TSCS testing in visits 3-6 by a questionnaire (**Appendix**). After every incremental increase of amplitude, investigator will ask participant if he/she is experiencing any symptoms. Maximum ramping amplitude will be 100 mA and testing will be halted if participant experiences any discomfort during testing. Based on preliminary work, regulation of neuromodulation of BP will occur at stimulation levels less than 100mA.

Participants will be notified by investigator if any of the findings from this study will affect the participants' health or welfare.

- Cardiovascular Assessments: While the subject is seated 3 ECG electrodes will be affixed to the chest and abdomen for continuous monitoring of HR and respiration rate (RR). Brachial BP will be monitored at 1 minute intervals using a standard adult BP cuff placed at the right upper arm, and beat-to-beat finger arteriolar BP will be continuously monitored from the right

middle finger throughout testing. Mean arterial pressure (mmHg) will be calculated from brachial BP using the formula: [systolic BP + (2\* diastolic BP)]/3. Beat-to-beat HR, RR and BP data will be viewed in real-time and stored for subsequent analysis using customized programs created with LabView graphical software.

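### Electrode site changes only between visits, but the SAP's only random effect is participant, so site differences are tested against reading-level rather than visit-level error

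*SAP*

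**What the plan says.** The SAP makes SBP the primary outcome and analyses it with a mixed model: "Participant will be modeled as a random effect and stimulation characteristics as fixed effects". The fixed effects include "cathodal stimulation site (T7/8, T9/10, T11/12, and L1/2") along with frequency, waveform, pulse width, carrier frequency and current. No visit, session or participant-by-site term is named, and no model formula is given.

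The protocol fixes the level at which site varies. Under Methods & Procedures, the paragraph on amplitude mapping at Visits 2-8 says: "Each visit, we will complete one electrode placement site". The general description of visits in the same section says: "there will be at least 3 days between study visits". The order of sites is randomized. The recruitment goal is 12 participants.

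Site is central to the study. The first hypothesis reads: "We hypothesize that electrode placement at the lower thoracic (T7/8) and 50 mA current will be the optimal parameters". Electrode site is also one of the two factors in the SAP's power calculation, which is justified in these words: "Given the number of repeated measurements of SBP in each participant, we anticipate having" 95% power for mean differences under 2 mmHg.

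**The concern.** Site is assigned to a visit, not to a reading. All readings at one site in one participant share whatever SBP level that participant had on that day. A model with a participant intercept alone removes the participant's long-run level but leaves the day's departure from it in the data. Because the whole visit used one site, that departure is attributed to the site, while the standard error shrinks with the number of readings as though each were independent.

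Two results are at stake. Confidence intervals for site contrasts are too narrow, so a best site can be declared when the sites do not differ. And the power claim, which rests on the count of readings, is too favourable for site, because more readings within a visit do nothing to reduce visit-level error. The same holds for any other stimulation factor kept constant within a visit; the documents do not say which of them are.

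**Working it through.** **Inputs from the documents.** 12 participants; 4 sites; one site per visit; 95% confidence level (two-sided assumed); target difference 2 mmHg with 95% power. Visits 2-8 are seven mapping visits for four sites, so both one and two visits per site were examined.

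**Inputs assumed, because no document gives them.** Visit SD within participant (σ_v) 0 to 5 mmHg; reading SD (σ_e) 6 or 8 mmHg; readings per visit (m) 5, 15 or 30.

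**1. The plan's own power figure.** It cannot be reproduced, since its variance inputs are not stated. It can be reached by counting readings as independent given participant. Readings per participant per site = 2σ_e²(1.96 + 1.645)² / 2² / 12, which is about 14, 35 or 54 for σ_e = 5, 8 or 10.

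**2. False-positive rate for site, one visit per site (48 visits).** When the sites do not differ:

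- Expected site mean square = σ_e² + mσ_v².
- Expected pooled residual in the participant-only model = [33(σ_e² + mσ_v²) + 48(m − 1)σ_e²] / [33 + 48(m − 1)], where 33 = (12 − 1)(4 − 1).

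Example with σ_v = 2, σ_e = 6, m = 15: the site mean square is 36 + 15 × 4 = 96, and the pooled residual is (33 × 96 + 672 × 36) / 705 = 38.8. The F statistic is inflated by 96 / 38.8 = 2.47. The chance that a chi-square on 3 df exceeds 7.81 / 2.47 is about 37%, in line with the 36% simulated.

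Simulation (4,000 null replicates per scenario), omnibus site test at nominal 5%:

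| Visit SD (mmHg) | Participant-only, m 5 to 15, σ_e 8 to 6 | Visit-level error |
|---|---|---|
| 0 | about 5% | 4% to 6% |
| 1 | 6% to 14% | 4% to 6% |
| 2 | 9% to 36% | 4% to 6% |
| 5 | 32% to 80% | 4% to 6% |

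With 30 readings of SD 6 and visit SD 5, the omnibus rate is 90% to 92% and a single pairwise contrast rejects in 59% to 61%. One or two visits per site gives nearly the same rates.

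**3. Power for 2 mmHg between two sites.** SE = √[2(σ_v² + σ_e²/m) / (12 × visits per site)], noncentral t with 33 df (one visit per site) or 81 df (two).

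- m = 30, σ_e = 6, one visit, σ_v = 0: SE = √(2 × 1.2 / 12) = 0.447; power 99%.
- Same with σ_v = 2: SE = √(2 × 5.2 / 12) = 0.931; power 55%.

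Ceilings with unlimited readings (m → ∞):

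| Visit SD (mmHg) | One visit per site | Two visits per site |
|---|---|---|
| 2 | SE 0.816, power 66% | SE 0.577, power 93% |
| 5 | SE 2.041, power 16% | SE 1.443, power 28% |

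The largest visit SD compatible with 95% power for 2 mmHg is 2 / [3.727 × √(2/12)] = 1.3 mmHg for one visit per site, or 2 / [3.654 × √(2/24)] = 1.9 mmHg for two. The multipliers are the sums of the 97.5% and 95% t quantiles.

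**4. Current, for contrast.** Current is ramped within a visit. With 11 steps from 0 to 100 mA and reading SD 6, the participant-only test of current rejects in 4.0%, 1.7% and 0.5% of null trials at visit SD 2, 5 and 8. It is conservative, not inflated. It rises to 6% to 10% only if the response slope also varies by visit (slope SD 5 mmHg per 100 mA, visit SD 0 to 5).

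**The case against.** The SAP is one paragraph without a formula. It does not exclude further random terms, and it refers to multi-level models for the power work. If random site slopes by participant were intended, then with one visit per site they would absorb the visit shift. The simr random structure is also unreported. All this is true, but no such term is stated, and if one is intended, writing it down is the remedy.

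The one-site-per-visit rule comes from the protocol, whose mapping procedure (30 Hz, 1-ms monophasic pulses, up to 100 mA) is narrower than the parameter grid in the SAP, and the SAP describes no visits. That mismatch is real. However, the protocol's visit structure is the only one documented, so the SAP has to be judged against it.

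The high error rates concern the site main effect on SBP itself. If sites were instead compared by their response to current, a shared visit shift would largely cancel. In simulation, the participant-only site-by-current test rejects in 5% of null trials at visit SD 0 to 1, 4% at SD 2 and 1% at SD 5. With visit-varying slopes it rejects in 6% to 16% (slope SD 5 mmHg per 100 mA) or 23% to 33% (slope SD 10). The SAP specifies no such interaction. Its current range includes 0 mA, but it does not identify that level with the same visit's pre-stimulation SBP; a comparison with baseline appears only for each participant's Cohen's d.

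Finally, visits are standardised (arrival time, breakfast, no alcohol or caffeine), ramping stops at an SBP target so reading counts will vary, and the visit SD is unknown. These points stand as limits on the size. They do not change the structure.

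**Conclusion.** The concern holds. As written, the model tests electrode site against the wrong error. This follows from the two documents alone and needs no outside figure. The size depends on assumed SDs and reading counts: there is no harm if visit-to-visit SD is zero, and the omnibus false-positive rate is several times nominal over much of the range from 2 to 5 mmHg. A near-zero visit SD would need justification here, because the protocol's literature review describes BP instability in this population, defined as SBP swings of more than 20 mmHg around the average. That is not a between-visit SD and was not used as one. Randomizing site order removes systematic bias but does not correct the standard error. The point must be fixed before analysis because site is in the first hypothesis. It does not extend to the test of current against visit-level shifts.

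**What to change.** Keep every declared fixed effect and write the random part out in full: `(1 | participant) + (1 | participant:visit)`. Add a by-visit random slope for current if the data support it. State that the 0 mA level is the same visit's pre-stimulation SBP. Use Kenward-Roger or Satterthwaite degrees of freedom for site contrasts. Rerun the simr calculation with the visit term; report the assumed visit SD, reading SD, readings per visit and visits per site; and restate the 95% power for differences under 2 mmHg.

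The cost is one model term, some SAP wording and a rerun of the power simulation, with no new data. Confidence intervals for site will be wider and the stated power lower. If visit variance proves negligible, the term is estimated near zero and little is lost.

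### As listed, the primary model lets stimulation site act at 0 mA and has no session-level term, so the site contrast is pulled toward zero and its standard error is too small

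*SAP*

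**What the plan says.** The SAP is one paragraph. On the outcome: "The primary outcome variable will be systolic blood pressure". On the model: "Participant will be modeled as a random effect and stimulation characteristics as fixed effects including", followed by a list that contains "cathodal stimulation site (T7/8, T9/10, T11/12, and L1/2") and "stimulation current (0–120mA"). No interaction, session term or baseline covariate is named. Baseline appears once, in the participant-level effect size (Cohen's d), where each participant's "blood pressure response will be compared to baseline blood pressure"; that baseline is not said to be session-specific.

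In the protocol (Methods & Procedures, paragraph on mapping visits 2-8), "Amplitude ramping will start at 10mA, with 10mA increments", up to 100 mA. One site is completed per visit, and "Continuous real-time BP and heart rate will be measured for 5-minutes, before, during and after stimulation". Visits are at least 3 days apart. The decision tree calls for a manual reading at about one minute per step, repeats it up to a third time when SBP has risen, and holds for 10 minutes once the target range is reached. The mapping paragraph also has the current stepped back down.

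**The concern.** No mapping step uses 0 mA, so a zero in the current variable can only be a reading with the stimulator off. Such a reading still belongs to a visit with an assigned site. A site cannot change SBP when no current flows, yet a site main effect applies to those rows as much as to the stimulated ones. The fitted contrast is then a mixture of the real difference and zero.

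The second issue arises from the same rows. Each site is measured on its own day. Any day-to-day shift in SBP moves every reading of that visit together, and a participant random effect cannot absorb it. The visit's own pre-stimulation recording would adjust for that shift, but the SAP does not use it that way in the primary model.

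At stake are the study's main purpose, finding which parameters raise SBP, and Hypothesis 1, which names T7/8 as the best site.

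**Working it through.** **1. The SAP's own figure.** The SAP expects 95% power for mean differences below 2 mmHg. It gives no SD, intraclass correlation or number of readings, so the figure can be neither reproduced nor refuted. Working backwards (2 mmHg, two-sided alpha 0.05, independent rows), 95% power needs 163, 416, 650 or 1,462 rows per site at SD 5, 8, 10 or 15 mmHg. More rows do not remove session variation. With one session per site in 12 participants and unlimited rows, a two-site comparison needs 2 / √(2s²/12) ≥ 1.960 + 1.645 = 3.605. The session SD s could then be at most 2 / (3.605 × 0.408) = 1.36 mmHg.

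**2. Share of 0 mA rows.** Share = zero rows / (zero rows + active rows), at one reading per minute:

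| Rows assumed to enter | Share |
|---|---|
| One 0 mA row, 10 steps | 1/11 = 9% |
| 5 before; 10 steps × 3 readings; 10-minute hold | 5/45 = 11% |
| 5 before + 5 after; 10 steps × 3 readings | 10/40 = 25% |
| 5 before; 10 steps | 5/15 = 33% |
| 5 before + 5 after; 10 steps | 10/20 = 50% |
| 5 before, 5 during, 5 after, taken literally | 10/15 = 67% |

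**3. Effect on the site contrast, equal ramps.** This is a noise-free fit of site + current, with assumed slopes of 0.2 and 0.1 mmHg per mA and ramps of 10 to 100 mA. The contrast on active rows is 0.1 × 55 = 5.5 mmHg. With 0 mA rows included it is 5.0, 3.67, 2.75 and 1.83 at shares of 9%, 33%, 50% and 67%. The ratios are 0.91, 0.67, 0.50 and 0.33, which is 1 − share each time. With site × current fitted, the site term at 0 mA is 0.0 and the slope difference of 0.10 is recovered exactly.

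**4. Unequal ramps.** The ramp stops on response, so ramps will differ between sites. Suppose one site stops at 50 mA (slope 0.4) and the other at 100 mA (slope 0.1):

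| Layout | Share | Loss, linear current | Loss, categorical current |
|---|---|---|---|
| 5 zero rows, no hold | 40% | 44% | 50% |
| 10 zero rows, no hold | 57% | 62% | 67% |
| 5 zero rows, 10-minute hold | 29% | 26% | 46% |
| 10 zero rows, 10-minute hold | 44% | 42% | 63% |

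**5. Power cost of the shrinkage alone.** Take a design with 95% power at the full effect and independent rows. Power after shrinkage is Φ(3.605 × (1 − share) − 1.960): 91%, 67%, 44% and 22% at shares of 9%, 33%, 50% and 67%. Part of this would be lost anyway, because dropping the 0 mA rows also costs rows: active rows alone give 84%, 72% and 55% at the last three shares.

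**6. Session variation.** Assume 12 participants, one session per site, 5 zero and 10 active rows per session, residual SD 8 and a true T7/8 advantage of 4 mmHg over the mean of the other three sites.

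- *Estimate.* Pooled rows give 4 × 10/15 = 2.7 mmHg; active rows give 4.0.
- *False positives.* The true variance of a session mean is s² + 64/15. The row-level fit uses (64 + 15s² × 33/704)/15. Here 33 is 48 sessions less 12 participant means and 3 site contrasts, and 704 is 720 rows less 16 parameters. At s = 4 this is 20.27 against 5.02, so the standard error is too small by a factor of 2.01 and null rejection is 2 × (1 − Φ(1.96/2.01)) = 33%. At s = 8 it is 68.27 against 7.27, a factor of 3.07 and 52%. Simulation gave 34% and 52%. Another layout (20 rows per session, residual SD 6) gave 49% and 63%.
- *Precision.* The contrast variance is V × (1 + 1/3)/12. For active rows V = s² + 6.4. With the session baseline as covariate V = 12.8s²/(s² + 12.8) + 6.4. For change from baseline V = 12.8 + 6.4.

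| Session SD | SE, active rows only | SE, baseline as covariate | SE, change from baseline |
|---|---|---|---|
| 0 | 0.84 | 0.84 | 1.46 |
| 4 | 1.58 | 1.23 | 1.46 |
| 8 | 2.80 | 1.38 | 1.46 |

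Simulation agrees to within rounding (for example 0.85 against 0.86 at session SD 0, where estimating the covariate slope costs almost nothing).

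**The case against.** The strongest reply is that this is a gap in specification and not a demonstrated bias. The SAP gives no formula. Its list is introduced as a list of inclusions, which leaves room for a site-by-current term, and such a term removes the shrinkage entirely. Nor does it say that the 5-minute recordings before and after stimulation are outcome rows; zero might only be the origin of the ramp, at about 9% of rows. This stands, and it is why the size can be given only as a range. It does not dispose of the point: a primary contrast should not depend on a choice that the plan leaves unstated, and a site-by-current term would not cure the missing session term.

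A reader might infer more than the documents support:

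- **That a third to a half of the rows are unstimulated.** Those shares come from particular layouts; the protocol's timings allow about 9% to 67%.
- **That the contrast always shrinks by exactly that share.** This needs an additive fit and equal ramps, and the stop-on-response rule makes ramps differ.
- **That baseline SBP is ignored.** It is used for Cohen's d and to steer the ramp, and 0 mA rows, if included, anchor the current effect. What is missing is a session-level adjustment in the primary model.
- **That most of the power is lost.** The loss depends on a session SD that is not given. In the row-level fit as listed, session variation shows up mainly as false positives.

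**Conclusion.** The point holds for the model as listed. In additive form, the site contrast is diluted by unstimulated rows: by 9% to 67% with equal ramps, and by 26% to 67% in the unequal-ramp cases tried. Separately, a participant-only random effect treats readings within a visit as independent, which gives about 34% to 52% null rejection at session SDs of 4 to 8 mmHg. The two faults do not cancel: one biases the estimate toward zero, the other overstates its certainty.

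The existence of the problem rests on the additive reading and, for the second part, on some day-to-day variation in SBP. The protocol's literature review reports blood pressure instability in this population, but gives no between-day SD. The sizes rest on assumed slopes, SDs, row counts and one session per site. Using the session baseline is a better method with data already collected, so this is more than a request for detail.

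**What to change.** In the SAP:

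1. Estimate the site effect only on rows with current above 0. Alternatively, fit site × current with no site effect allowed at 0 mA.
2. Enter each session's mean 5-minute pre-stimulation SBP as a covariate. If the alternative in item 1 is chosen and those readings stay in as outcome rows, do not also use them as the covariate.
3. Prefer the covariate to change from baseline. Change from baseline loses precision when session variation is small (SE about 1.5 against 0.85 at session SD 0).
4. Keep post-stimulation rows out of the site contrast, and state whether ramp-down and hold rows enter.
5. Add a random effect for session within participant.
6. Rerun the power simulation with that session effect, and report the SDs and row counts used.

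No new data are needed. The cost is slightly more modelling, and intervals wider than those of the participant-only fit, because they then reflect day-to-day variation.

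### The per-participant Cohen's d has no defined readings, window, SD or interval method; a default independence interval on serial SBP readings would be too narrow, and d would change with the averaging window

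*SAP*

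**What the plan says.** The SAP is a single section. After the mixed model, it adds a separate calculation for each participant's best parameters: the "blood pressure response will be compared to baseline blood pressure to calculate" Cohen's d, with confidence intervals. It then states, for all analyses, that "The 95% level of confidence will be used". It gives no formula for d, no unit of observation, no window, no standardising SD and no method for the interval. Its only provision for correlation is "Participant will be modeled as a random effect", which belongs to the mixed model.

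The protocol shows which readings exist. Methods & Procedures describes mapping sessions "with continuous beat-to-beat BP monitoring at the finger arteriole and at 1-minute intervals at the brachial artery". The paragraph on amplitude mapping (visits 2 to 8) gives five-minute recording periods around and during stimulation and one electrode site per visit. The TSCS decision tree adds manual readings about a minute apart at each current step, and a 10-minute hold once the target range is reached. No repeat of a site on a second visit is described.

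**The concern.** A d computed within one person has only that person's readings as replicates, and here these are mostly consecutive readings from a session. Two problems follow.

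- **Interval.** The textbook interval for d takes the readings as independent. Positive serial correlation means that they carry less information than their count suggests, so the interval is too short. The participant random effect cannot repair this, because the d calculation sits outside the mixed model.
- **Scale of d.** The divisor is the reading-to-reading SD, which shrinks as readings are averaged over longer windows. The same rise in mmHg therefore gives a different d on beats and on minute means. Even with a common window, it differs between participants whose autocorrelation differs.

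The trial's objective is an individualised map, and these are the only individual-level effect estimates in the SAP. At stake is whether random variation within a session is reported as a clear individual response, and whether the values can be compared between participants.

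**Working it through.** **The plan's own figure.** The SAP gives no figure for the d intervals. Its one figure, "95% power to detect <2-mm-Hg mean differences at the 95% level of confidence", belongs to the mixed model and is justified by "Given the number of repeated measurements of SBP in each participant". It cannot be reproduced, because no SD, variance components or number of readings is stated. With independent readings, n per condition = 2 × SD² × (1.96 + 1.645)² / 2², which is 163 at SD 5, 650 at SD 10 and 1,462 at SD 15 mmHg. That figure neither supports nor refutes this point.

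**Inputs from the documents.** Five-minute recording periods; continuous beat-to-beat pressure; brachial readings each minute; 95% confidence; planned sample size ("It is our goal to recruit 12 eligible hypotensive individuals").

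**Assumptions, not in the documents.** Heart rate 70/min, so 5 × 70 = 350 beats per period; AR(1) readings with lag-1 correlation ρ from 0.3 to 0.95; the standard interval d ± 1.96 × √[(n₁+n₂)/(n₁n₂) + d²/(2(n₁+n₂))].

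**Step 1: interval on raw beats.** The variance of a mean of n readings is inflated by V = 1 + 2Σ(1 − k/n)ρᵏ, summed over k = 1 to n − 1. The interval is too narrow by √V. At true d = 0, coverage is close to 2Φ(1.96/√V) − 1.

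| ρ (beats) | √V, n = 350 | 1.96/√V | Coverage |
|---|---|---|---|
| 0 | 1.00 | 1.96 | 95% |
| 0.3 | 1.36 | 1.44 | 85% |
| 0.5 | 1.73 | 1.13 | 74% |
| 0.8 | 2.98 | 0.66 | 49% |
| 0.9 | 4.30 | 0.46 | 35% |

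Simulation of paired AR(1) series agrees to within about two percentage points. With no true effect, about 25% of intervals exclude zero at ρ = 0.5 and about 67% at ρ = 0.9. For 12 such participants that is 12 × 0.25 = 3 to 12 × 0.67 = 8.

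**Step 2: the same signal on a one-minute scale.** The correlation between two beats one minute apart is 0.9⁷⁰ = 0.0006, or 0.95⁷⁰ = 0.028, so spot cuff readings under this model are nearly independent and simulated coverage is 93% to 95%. One-minute means have lag-1 correlation of about 0.03, 0.08 and 0.18 at beat ρ of 0.8, 0.9 and 0.95. Simulated coverage with five or ten means per period is about 94%, 93% and 90%.

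**Step 3: slow drift.** If drift adds correlation between minutes, coverage falls again. For five readings against five at true d = 0 it is about 85%, 74% and 57% at minute-to-minute correlation 0.3, 0.5 and 0.7. This is a separate assumption; it does not follow from Step 1.

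**Step 4: d and the averaging window.** Averaging m beats multiplies d by √(m/V), with V computed at n = m. For m = 70:

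- ρ = 0.9: V = 16.43 and √(70/16.43) = 2.06. A rise of 8 mmHg with a beat SD of 10 (both illustrative) is d = 0.8 on beats and 0.8 × 2.06 = 1.65 on one-minute means.
- ρ = 0.5: V = 2.94 and √(70/2.94) = 4.88, so the same rise becomes 0.8 × 4.88 = 3.90.

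Two participants with the same rise and the same beat SD would thus show 1.65 and 3.90 on one-minute means, solely because their autocorrelation differs.

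**The case against.** The strongest reply is that the SAP nowhere says the readings will be treated as independent. A reader might infer from its silence that the intervals are invalid and far too narrow. The documents do not support that: no interval method is fixed, and no autocorrelation is given. This part of the objection stands, and the coverage figures are conditional on it.

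Three further points carry weight.

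- The severe under-coverage belongs to raw beats. If d is built from minute readings, an AR(1) beat signal leaves the interval close to nominal unless there is drift.
- A reader might infer that all of a participant's readings come from one session. Seven mapping visits for four sites at one site per visit leave 7 − 4 = 3 visits over, so repeats are possible, although none is described.
- A reader might take these intervals as the rule by which a setting is declared to work. The SAP uses d only to quantify effect size, and the decision tree defines a sustained response by manual readings in a target range. No decision rests on d excluding zero.

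The objection does not dispose of the point. Computing a standard d and interval on serial readings, which the SAP's wording permits, under-covers at every positive correlation tested. The dependence of d on the window remains whichever interval is used.

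**Conclusion.** The point holds in conditional form. The SAP commits to a 95% interval for each participant's d without naming the readings, window, SD or treatment of serial correlation. If the default independence formula is used on beats, coverage falls to about 85% at ρ = 0.3 and 35% at ρ = 0.9. On one-minute means of the same signal the loss is small, at about 90% to 94% coverage for ρ of 0.8 to 0.95, unless slow drift is present. These figures rest on AR(1) errors, a heart rate of 70/min and assumed values of ρ.

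The second part needs no particular ρ: d depends on the averaging window and on each participant's own autocorrelation, so it is not a common scale for comparing participants.

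The consequence is confined to a descriptive individual-level summary. This calculation does not bear on the primary mixed model or its stated power. It should still be settled before analysis, because individual responses are what the trial sets out to map.

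**What to change.** Replace the sentence on Cohen's d with a specification along these lines:

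1. Report each participant's response as the mean change in SBP in mmHg, optimal setting minus baseline, from a named reading source (finger or brachial) and named windows for both periods.
2. Compute the 95% interval from one-minute or per-step means with a method that allows for serial correlation, either AR(1) errors or a block bootstrap. Five or ten means per period estimate a correlation poorly, so consider a correlation parameter pooled across participants. If sites are repeated on separate visits, use session-level means.
3. If a standardised effect is kept, name in advance a between-session or between-participant SD as the divisor.
4. State that the interval does not correct for the optimal setting having been selected on the same SBP readings. Neither AR(1) errors nor a block bootstrap removes that bias.

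The cost is a few sentences in the SAP and a few lines of R; no extra data are needed. The downside is that intervals will usually be wider, and some individual responses will look less certain than under the default formula.
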